5.3.4 Treatment or Action Taken

Action taken in response to an adverse event shall be recorded as:

- None
- OTC or Rx drug added
- Non-drug treatment/procedure
- Hospitalization or ER visit

Action taken with study procedure shall be recorded as:

- None
- Study procedure interrupted
- Study procedure discontinued

5.3.5 Outcome

The clinical outcome of an AE shall be characterized as follows:

- Resolved without sequelae
- Resolved with sequelae (specify)
- Ongoing (i.e. continuing at time of study discontinuation)
- Death
- Unknown

5.4 RISK ANALYSIS & ANTICIPATED ADVERSE EVENTS

5.4.1 Risk Analysis

Risks associated with using the iLux 2020 were assessed in accordance with ISO 14971, which is an international standard for medical device risk management that is recognized by the FDA. Most of the potential hazards identified in the analysis are common to many medical devices and are addressed by compliance with international standards. Other potential hazards unique to the iLux were addressed by assessing risk using Failure Modes Effects and Criticality Analysis (FMECA) and identifying controls to reduce residual risks to acceptable levels.

The iLux is used in the eye and the sterile disposable may come in contact with the conjunctiva and or cornea during the treatment of each lid. The sterile disposable is covered with a biocompatible silicone similar to a contact lens. There is nothing implanted either temporarily or permanently in the eye related to the iLux and the risk is similar to other meibomian gland treatments. Testing demonstrated that the disposable meets the requirements for biocompatibility (ISO 10993) and sterilization and packaging (ISO 1135, ISO 11607).

Compliance to IEC 60601-1, which is an international standard for safety of electromedical devices, was evaluated by the nationally recognized test laboratory, Nemko. As part of the evaluation, the risk management files were reviewed to verify compliance with ISO 14971. Other IEC 60601-1 tests included electromagnetic compatibility (IEC 60101-1-2) and optical radiation safety (IEC 62471). The iLux system successfully met the requirements of all tests performed.

The instrument warms the eyelids using optical radiation (i.e., light) at two wavelengths, lime-green and infrared. Potential photobiological hazards were evaluated by [name], who is an internationally-respected expert in the field of optical radiation hazards and consults frequently with both the FDA and industry. His testing was also witnessed by an expert from Nemko for certification to the standard IEC 62471. Their analysis concluded that the iLux system poses minimal risk for damage to the eye or skin and can be classified as exempt from warnings. To further reduce risk, the heating cannot be operated without a disposable attached, which blocks a significant portion of the emitted light.

A safety study was conducted at Absorption Systems in San Diego from November to December, 2014. The study involved exposing one shaved eyelid on each of four New Zealand white rabbits to the same energy wavelengths and levels that are emitted by the iLux device, using a back plate and front plate similar to the human device, and applying a controlled force to the eyelids. One cohort received two-minute treatments and the other received four-minute treatments, with each treatment applied once per week for five treatments. No adverse events occurred and there were no changes observed in the eyelids or eyes, and there were no adverse histological findings.

The iLux system measures temperatures on the inner and outer surfaces of the eyelid. Four redundant temperature sensors are included in the disposable. The instrument displays the highest inner eyelid temperature. If any of the four sensor readings exceeds 44 °C, the instrument automatically turns off the heat source. Bench top testing has shown that the back plate of the iLux disposable tip does not heat above 40°C.

Lastly, the iLux system was recently used on 30 subjects in an IRB approved, non-significant risk study in the United States with no adverse events.

The mitigations taken demonstrate that the risk of any adverse effects on study subjects participating in this study have been eliminated or minimized to the extent possible and therefore, the risk to study subjects is acceptable for this study.

5.4.2 Anticipated Adverse Events

- Eyelid/eye Pain
- Eyelid Irritation or Inflammation
- Ocular Surface Irritation or Inflammation
- Ocular Symptoms Burning, stinging, tearing, itching, discharge, redness, foreign body sensation, visual disturbance, sensitivity to light.

5.5 SERIOUS ADVERSE EVENT AND UNANTICIPATED ADVERSE DEVICE EFFECT REPORTING

SAEs and unanticipated adverse device effects (UADE) must be reported to the study sponsor (Tear Film Innovations, Inc.) and study Principal Investigator (PI) as soon as possible and no later than **24 hours** after the investigator first learns of the event.

For initial reports, Investigators shall record all case details that can be gathered within the reporting timeframe. The contact information for Tear Film Innovations, Inc. and the PI is below:

Study Sponsor:

Relevant follow-up information shall be submitted to the sponsor as soon as it becomes available and/or upon request. For some events, the sponsor or his designee may follow up with the site by telephone, fax, electronic mail, and/or a monitoring visit to obtain additional case details deemed necessary to appropriately evaluate the event (e.g., hospital discharge summary, consultant report, or autopsy report). Reports relating to the subject's subsequent medical course must be submitted to the study sponsor until the event has subsided or, in case of permanent impairment, until the event stabilizes and the overall clinical outcome has been ascertained.

6 STUDY DISCONTINUATION

The study sponsor has the right to terminate this study at any time. Reasons for terminating the study may include, but are not limited to, the following:

- The incidence or severity of adverse events in this or other studies indicates a potential health hazard to subjects
- Subject enrollment is unsatisfactory
- Data recording is inaccurate or incomplete.

7 STATISTICAL PLAN

No formal hypotheses will be used in this study. Subject demographic characteristics and background variables shall be summarized.

Pre-treatment, post-treatment and maximum treatment temperatures will be summarized with N, mean, standard deviation, minima, maxima, median, and interquartile range. The maximum change recorded will be similarly summarized.

All subjects enrolled and treated in the study shall be included as part of the safety analysis.

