7.1 EFFICACY ENDPOINTS

The primary efficacy endpoint of this trial is the temperature of the cornea and the surrounding eye tissue after heating with the iLux instrument.

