7.2 SAMPLE SIZE JUSTIFICATION

A sample size of 15 subjects (30 eyes) has been chosen for an initial assessment of the safety of the iLux System in this patient population. This number was chosen to provide sufficient data to make an initial safety determination of the System while minimizing the number of patients subjected to a clinical trial.

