7.3 SAFETY

AEs, SAEs, and other findings shall be summarized by presenting the number and percentages of subjects with each event. Continuous endpoints shall be summarized using summary statistics such as means, medians, standard deviations, minima, maxima, and relevant percentiles.

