Adnexa	0 0 1 0 2	0 0 1 0 2		_	
Conjunctiva	0 0 1 0 2	0 0 1 2			
Sclera	0 0 1 0 2	0 1 2			
Corneal clarity	0 1 2	0 0 1 0 2			
Tear film	0 0 1 0 2	0 0 1 0 2			
Anterior chamber	0 0 1 0 2	0 0 1 0 2			
Iris	0 1 2	0 1 2			
Intraocular Pressure	OD	os			
Goldmann (mmHg)			_		
Lid Margin Assessment	C	heck "Yes" for each c	condition that applies to each	ı lid	
		er Lid		ver Lid	
0=None 1=Irregular Lid Margin 2=Vascular Engorgement 3=Ant/Post Replacement of	OD Yes No Yes No Yes No	OS Yes No Yes No Yes No	OD Yes No Yes No Yes No	OS ☐ Yes ☐ No ☐ Yes ☐ No ☐ Yes ☐ No	
Mucocutaneous Junction	☐ Yes ☐ No	☐ Yes ☐ No	☐ Yes ☐ No	☐ Yes ☐ No	

[figure not shown]

FORM 4: OCULAR ASSESSMENT - Page 2 of 2

Corneal Fluorescein Staining Grading

Enter the staining grade for each segment of each eye

0 = Normal; No staining

1 = Mild; Superficial staining, micropunctate staining

2 = Moderate; Macropunctate staining with some coalescent areas

3 = Severe; Numerous macropunctate areas and/or patches

Manifest Refraction	+/-	Sphere	Cylinder	Axis
OD				X
OS			-	X
Keratotomy	OD			OS
Steep	D	0		D0
Flat	D	0		D0
Eve Temperature Assessment		OD	OS	
1st Reading - Pre-Treatment and Post-	-Treatment			
Corneal Temp (close eye for 5 sec, the	n open)			_
Surrounding Tissue Temp (close eye for	or 5 sec)			
2nd Reading - Post-Treatment Only	_			
Corneal Temp (close eye for 5 sec, the	n open)			_
Surrounding Tissue Temp (close eye f	or 5 sec)			
3rd Reading- Post-Treatment Only				_
Corneal Temp (close eye for 5 sec, the	n open)			_
Surrounding Tissue Temp (close eye for	or 5 sec)			_

FORM 5: PAIN/DISCOMFORT ASSESSMENT- Page 1 of 1

Assessment Date (DD-MMM-YYYY)				
Assessment Timeframe	☐ Pre-Treatment ☐ Post-Treatment ☐ Follow-Up			
Assessment Intertaine	☐ Other, please specify:			
	OD	os		
Subject's pain level (scale 0-10)				

Score	Level of Discomfort/Pain	Description to Anchor Subjective Response	
0	No discomfort or pain	Minimal recognition of pressure only. Equal to the touch of a finger on the skin. Awareness but no discomfort.	
2	Slight or transient awareness of pressure without pain	Pressure tolerable and could be endured indefinitely without compromise to daily activities. Examples: bruise; medical injection; wearing dress shoes, which one would wear all day and might forget to remove when returning home; poorly adjusted glasses.	

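### Must Section 7 name the Form 4 reading that counts as the post-treatment temperature, and say how the maximum change is formed?

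*Combined protocol and SAP*

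**What the plan says.** Section 7 tests no hypothesis. Its temperature analysis is two sentences: "Pre-treatment, post-treatment and maximum treatment temperatures will be summarized with N, mean, standard deviation, minima, maxima, median, and interquartile range", followed by "The maximum change recorded will be similarly summarized". Section 7.1 adds that "The primary efficacy endpoint of this trial is the temperature of the cornea and the surrounding eye tissue after heating" with the device. Section 7.2 gives the size in both units: "A sample size of 15 subjects (30 eyes) has been chosen". Section 7.3 names a unit for events only: "AEs, SAEs, and other findings shall be summarized by presenting the number and percentages of subjects with each event".

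The values come from two forms in the case report form appendix. The eye temperature block of Form 4 has three entries: "1st Reading - Pre-Treatment and Post"-Treatment, "2nd Reading - Post-Treatment Only" and "3rd Reading- Post-Treatment Only". Each has one line for the cornea and one for surrounding tissue, with OD and OS columns. Form 6 records a maximum temperature for each of four lid zones in each eye.

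Sections 2.1 and 2.2 place the measurement and the primary analysis immediately after heating. Section 2.2 also has the Appendix 1 parameters, temperature among them, evaluated eye by eye.

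**The concern.** The primary endpoint is a temperature after heating, yet each site in each eye has three such temperatures. Section 7 does not say whether the post-treatment value is the first, the last, the mean or the highest. It does not say over what the maximum change is taken, or whether N counts subjects or eyes. Nor does it say whether the Form 6 maximum is shown per zone or as the highest of four.

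Two analysts could therefore produce different N, means and SDs from identical forms, and the rule could be picked after the readings are seen. These summaries are the study's main quantitative result. Also, the largest of three noisy readings set against one baseline tends to exceed a single-reading change even when nothing has changed.

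**Working it through.** **The plan's own figure.** 15 subjects × 2 eyes = 30 eyes, as Section 7.2 states. No power or precision figure is given, so there is none to reproduce.

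**Values on the forms, per subject**
- Form 4, pre-treatment: 1 reading × 2 sites × 2 eyes = 4; over 15 subjects, 60.
- Form 4, post-treatment: 3 × 2 × 2 = 12; over 15 subjects, 180.
- Form 6 maxima: 4 zones × 2 eyes = 8; over 15 subjects, 120.

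**What the documents settle, item by item**

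| Open item | Evidence elsewhere | What is left |
|---|---|---|
| Unit | Section 2.2 evaluates each eye; Section 7.2 counts 30 eyes; Forms 4 and 6 have OD and OS columns | The eye is the natural row unit (N = 30). N = 15 would need averaging or selecting within a subject, which is not mentioned |
| Site | Section 7.1 names two sites; Form 4 gives each its own line | N = 60 or 180 arises only by pooling cornea with surrounding tissue, which nothing suggests |
| Reading | Sections 2.1 and 2.2 stress the immediate value | Reading 1 is favoured but not stated. Section 7 speaks of temperatures in the plural, so one row per reading also complies |
| Maximum treatment temperature | Form 6 has a maximum temperature field under the treatment heading | Per zone or highest of four |
| Maximum change | Form 4 is the only form with numerical values both before and after; Form 6 has only a tick box for the baseline | Largest post-treatment reading minus baseline is the like-for-like choice, but unwritten |

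**Size of the difference between rules.** Let s be the SD of one reading, with independent normal errors, and d the true fall from one reading to the next. The documents give neither. The baseline is common to all three differences and cancels, so the excess of the maximum over the first reading is E[max(Z1, Z2 − d, Z3 − 2d)], in units of s. The true mean of three lies d below the first reading, so the excess over the mean of three is that value plus d.

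| d (in s) | Max minus first reading | Max minus mean of three |
|---|---|---|
| 0 | 0.846 | 0.846 |
| 0.5 | 0.449 | 0.949 |
| 1 | 0.225 | 1.225 |
| 2 | 0.051 | 2.051 |

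For an assumed s of 0.1 to 0.5 °C and no drift: 0.846 × 0.1 = 0.08 °C and 0.846 × 0.5 = 0.42 °C. If the eye warms between readings, the maximum exceeds reading 1 by more. At d = −0.5 s the excess is 0.949 + 0.5 ≈ 1.45 s, much of it a true rise.

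**Cooling illustration, all values assumed.** Take a true rise of 2 °C, s = 0.3 °C, and cooling of 0.2, 0.5 or 1.0 °C per reading.

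| Cooling per reading | Reading 1 | Mean of three | Reading 3 | Maximum |
|---|---|---|---|---|
| 0.2 °C | 2.0 | 1.8 | 1.6 | 2.11 |
| 0.5 °C | 2.0 | 1.5 | 1.0 | 2.03 |
| 1.0 °C | 2.0 | 1.0 | 0.0 | 2.00 |

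The two rules that the text favours, the immediate reading and the maximum, agree here to about 0.1 °C. The rules that diverge, the mean and the last reading, are the ones the stress on immediacy points away from.

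**The case for a change.** The best argument for a change is that these summaries carry the study's stated objective and that two or three sentences would remove the doubt. A descriptive study has no test to fall back on, so its definitions are all it has. Section 2.2 speaks of assessments in the plural and never says that reading 1 is the analysis value. A mean of three or a last reading, chosen after the fact, could show a smaller rise than the eye experienced.

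Part of this stands. No rule for the three readings, for the maximum change or for the four zone maxima appears in Sections 7 to 7.3, and the sizes above show that the rules can differ.

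The consequence does not follow. There is no test, error rate or pass mark for a later choice to distort, and the documents attach no temperature limit to this endpoint. A favourable choice for the post-treatment row would not hide the peak, because the plan separately commits to the maximum change. Used as a safety summary, a maximum of several readings leans towards overstating heating, and the plan already calls it a maximum.

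Step 9 of Section 3.1, which governs the camera readings, breaks off in the public text. It cannot be held against the plan that this step does not say which reading the ten-second window covers.

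**Conclusion.** No change to the plan follows. This is missing detail that an analyst would fill sensibly from the rest of the document: one row per eye, cornea and surrounding tissue apart, readings 1 to 3 shown by number, and the maximum change taken as the largest post-treatment reading minus the single baseline. All of that complies with Section 7 as written. With 30 eyes, every reading can also be listed.

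What remains open is the choice among three readings, the exact formation of the maximum change, and whether the zone maxima are shown separately. Choosing the maximum over the first reading adds at most 0.85 s on average when there is no drift or cooling, or 0.08 to 0.42 °C for s of 0.1 to 0.5 °C. This rests on independent normal errors and on an assumed s that the documents do not supply. Under warming the gap is larger but partly real. No hypothesis, threshold or planned decision depends on it, and the safety reading of the study is not made less cautious.

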7.1 EFFICACY ENDPOINTS

The primary efficacy endpoint of this trial is the temperature of the cornea and the surrounding eye tissue after heating with the iLux instrument.

7.2 SAMPLE SIZE JUSTIFICATION

A sample size of 15 subjects (30 eyes) has been chosen for an initial assessment of the safety of the iLux System in this patient population. This number was chosen to provide sufficient data to make an initial safety determination of the System while minimizing the number of patients subjected to a clinical trial.

7.3 SAFETY

AEs, SAEs, and other findings shall be summarized by presenting the number and percentages of subjects with each event. Continuous endpoints shall be summarized using summary statistics such as means, medians, standard deviations, minima, maxima, and relevant percentiles.

8 RECORD RETENTION

The investigator shall maintain all subject records for a period of two years after the investigation is discontinued and FDA is notified.

The investigator must maintain accurate records of the receipt of all investigational material shipped by the sponsor, including the date and lot numbers received. In addition, accurate records must be kept on the amount and date that the investigational material, by lot number, was used and for each subject.

The investigator must assure that study supplies are used only in conjunction with subjects enrolled in the study and under the direct supervision of the investigator or co-investigators.

9 STUDY MONITORING REQUIREMENTS

It is the responsibility of the study sponsor, Tear Film Innovations, Inc., to ensure proper monitoring of the investigation and to see that all the clinical requirements are met. Either Tear Film personnel or a contracted third party will perform monitoring. In general, monitoring will consist of an initiation visit to train the site on the proper use of the device and execution of the protocol. Due to the small size of the study and the limited data being collected, monitoring will likely consist of 1-2 visits to the site to compare study CRF data with site source data. During these visits, the monitor may review the subject records to verify that all records and files are current and to assure compliance with all requirements of this protocol. The final monitoring visit may also serve as the study close-out visit.

10 PROTOCOL DEVIATIONS/AMENDMENTS

An investigator may deviate from the protocol to protect the life or physical well-being of a subject in an emergency, and must notify the sponsor and the reviewing IRB within 5 working days after the emergency occurred. Except in such an emergency, an investigator may not deviate from the protocol unless he/she obtains the prior approval of Tear Film

Innovations, Inc. Depending on the specifics of the deviation, IRB approval may also be required.

Page 39 of 65

APPENDIX 1: SCHEDULE OF ASSESSMENTS

[figure not shown]
	PRE-	TREATMENT	POST-	FOLLOW UP
ASSESSMENT	TREATMENT		TREATMENT	
Treatment Window	Day 0	Day 0	Day 0	Day 1 (-0/+3 davs)
Informed Consent	X			•
Demographics/medical/ocular history	X			
Visual Acuity	X		X	
Slit Lamp for Anterior Segment health	X		X	
Lid Margin Abnormalities	X		X	
Corneal fluorescein staining slit lamp evaluation	X		X	
Intraocular pressure	X		×	
Cornea and surrounding eye tissue temperature	X		X	
iLux heating		X		
Discomfort/pain questionnaire	X		X	X
Adverse Events		X	X	X

APPENDIX 2: ILUX USER MANUAL

APPENDIX 3: CORNEAL FLUORESCEIN STAINING PROTOCOL

APPENDIX 4: GENERAL MEDICAL AND OPHTHALMIC HISTORY

QO		SO
Degree of Staining	Region	Degree of Staining
123	C - Central	0123
123	S - Superior	0123
123	T - Temporal	0123
123	N - Nasal	0123
123	1 - Inferior	0123

Grade 0 = Normal	No staining	
Grade 1 = Mild	Superficial stippling micropunctate staining	27 O 17
Grade 2 = Moderate	Macropunctate staining with some coalescent areas	Fage 41 01 05
Grade 3 = Severe	Numerous coalescent macropunctate areas and/or patches	

Appendix 2: Case Report Forms

SUBJECT 1	ID:	-	

FORM 1: INCLUSION/EXCLUSION - Page 1 of 1

Screening/Pre-Treatment Date (DD-MMM-YYYY)	
Did subject meet all inclusion and no exclusion criteria? If no, indicate which criteria the subject did not meet:	☐ Yes ☐ No
Inclusion criterion #/criteria #s not met:	
Exclusion criterion #/criteria #s not met:	
Was Sponsor notified of protocol deviation?	☐ Yes ☐ No ☐ N/A
Was IRB notified of protocol deviation?	☐ Yes ☐ No ☐ N/A
Did subject sign an informed consent form?	☐ Yes ☐ No
If "Yes", please provide date signed (DD-MMM-YYYY)	

Subject Assessment Schedule:

ASSESSMENT	PRE- TREATMENT	TREATMENT	POST- TREATMENT	FOLLOW UP
Treatment Window	Day 0	Day 0	Day 0	Day 1 (-0/+3 days)
Informed Consent	X			
Demographics/medical/ocular history	X			
Visual Acuity	X		X	
Slit Lamp for Anterior Segment health	X		X	
Lid Margin Abnormalities	X		X	
Corneal fluorescein staining slit lamp evaluation	X		X	
Intraocular pressure	X		X	
Cornea and surrounding eye tissue temperature	X		X	
iLux heating		X		
Discomfort/pain questionnaire	X		X	X
Adverse Events		X	X	X

Required Case Report Forms by Assessment:

Pre-Treatment	Forms 1-5	
Treatment	Forms 6-7	Form 8 with any Adverse Event Form 9 with Device Event
Post-Treatment	Forms 4-5	Form 8 with any Adverse Event
Follow-Up	Form 5	Form 8 with any Adverse Event

SUBJECT ID:	_

FORM 2: DEMOGRAPHICS & MEDICAL HISTORY- Page 1 of 1

Demographics:				
Date of birth (DD-MMM-YY Gender Ethnicity Race	□ Male □ Femal□ Hispanic or Lat□ American India	ino 🛭 Not Hispan	🗖 Asian 🗖 Black or African An	nerican
Medical History Does the subject have: Diabetes? Hypertension? Hypercholesterolemia? Allergies to medication? Infection disease (HIV, TB)?		# of Years	Treated w/ Medication? Yes No	
List all medications subject is	-	, please specify:	opathic, birth control, or remedies	
List all major injuries, surgeri	es, and/or hospitaliz	ations subject has	had:	
Does the subject drive? Does the subject have difficult	ty driving?	☐ Yes ☐ No ☐ Yes ☐ No		
If Yes, please explain: Does the subject use tobacco Does the subject use alcohol p Does the subject use illicit dru	products?	Yes No Yes No Yes No		
PCP Name:				
PCP Phone #:				
Last Medical Exam Is the subject currently under If yes, please specify:	- medical care for any	- v condition?	(DD-MMM-YYYY) ☐ Yes ☐ No	

SUBJECT ID:	_
-------------	---

FORM 3: SYMPTOMS & OCULAR HISTORY- Page 1 of 1

Subject General Symptoms		Subject Ocular Symp	toms	Which Eye?
Constitutional: Fever, Weight Loss, Appetite	☐ Yes ☐ No	Sudden Vision Loss	☐ Yes ☐ No	□ OD □ OS
Integumentary: Skin conditions/ disorders	☐ Yes ☐ No	Blurred Vision	☐ Yes ☐ No	OD OS
Neurological: Headaches, Migraine, Seizures	☐ Yes ☐ No	Loss of Side Vision	☐ Yes ☐ No	□ OD □ OS
Ear, Nose, Throat: Allergies, Sinus, Cough,	☐ Yes ☐ No	Double Vision	☐ Yes ☐ No	□ OD □ OS
Dry Throat/Mouth		Floaters	☐ Yes ☐ No	□ OD □ OS
Respiratory: Asthma, Emphysema, Bronchitis	☐ Yes ☐ No	Flashes	☐ Yes ☐ No	□ OD □ OS
Vascular: Hypertension, Stroke, Heart Pain	☐ Yes ☐ No	Mucus Discharge	☐ Yes ☐ No	□ OD □ OS
Gastrointestinal: Diarrhea, Constipation	☐ Yes ☐ No	Redness	☐ Yes ☐ No	□ OD □ OS
Genitourinary: Genitals, Kidneys, Bladder	☐ Yes ☐ No	Gritty Feeling	☐ Yes ☐ No	□ OD □ OS
Bones/ Joints: Rheumat Arthritis, Muscle Pain	☐ Yes ☐ No	Itchy/Burning	☐ Yes ☐ No	□ OD □ OS
Lymphatic/Hematologic : Anemia, Bleeding	☐ Yes ☐ No	Tearing/Watery	☐ Yes ☐ No	□ OD □ OS
Allergic Immunologic: Allergies, Immune	☐ Yes ☐ No	Glare	☐ Yes ☐ No	□ OD □ OS
Psychiatric: Depression/Anxiety	☐ Yes ☐ No	Eye Pain/Discomfort	☐ Yes ☐ No	□ OD □ OS
		Haloes at Night	☐ Yes ☐ No	□ OD □ OS
Family Medical and Ocular History		Relative/Relationship	):	
DE 1				
Blindness	☐ Yes ☐ No			
Cataracts	☐ Yes ☐ No			
Cataracts	a 163 a 110			
Glaucoma	☐ Yes ☐ No			
Macular Degeneration	☐ Yes ☐ No			
Retinal Disease	☐ Yes ☐ No			
Arthritis	☐ Yes ☐ No			
Company	D Ves D Ne			
Cancer	☐ Yes ☐ No			
Diabetes	☐ Yes ☐ No			
Diabetes	a res a no			
Hypertension	☐ Yes ☐ No			
Trypercension	— 165 — 110			
Heart Disease	☐ Yes ☐ No			
	_ 100 _ 110			
Kidney Disease	☐ Yes ☐ No			
22.02.07	_ 133 _113			
Thyroid Disease	☐ Yes ☐ No			
•				
Other:	☐ Yes ☐ No			
Dlagg gracify				
Please specify:				

SUBJECT	ID:	-

[figure not shown]
FORM 4: OCULAR ASSESSMENT - Page 1 of 2					
Assessment Timeframe					
Visual Acuity	Total ETDRS	Letters Read			
Uncorrected	OD	os	OD ☐ Finger Count OR ☐ Hand Movement ☐ Light Perception	OS ☐ Finger Count ☐ Hand Movement ☐ Light Perception	
Habitual correction Best correction			OR Hand Movement Light Perception Finger Count OR Hand Movement Light Perception Light Perception	☐ Finger Count ☐ Hand Movement ☐ Light Perception ☐ Finger Count ☐ Hand Movement ☐ Light Perception	
Slit Lamp Examination		A . 7. I. A .			
0 = No Clinical Finding; 1 =	: Non-Clinically Signi OD	ficant Finding; 2 = A OS	lbnormal Finding; if > 0, p l OD	lease specify below : OS	
Adnexa	0 0 1 0 2	0 0 1 0 2		_	
Conjunctiva	0 0 1 0 2	0 0 1 2			
Sclera	0 0 1 0 2	0 1 2			
Corneal clarity	0 1 2	0 0 1 0 2			
Tear film	0 0 1 0 2	0 0 1 0 2			
Anterior chamber	0 0 1 0 2	0 0 1 0 2			
Iris	0 1 2	0 1 2			
Intraocular Pressure	OD	os			
Goldmann (mmHg)			_		
Lid Margin Assessment	C	heck "Yes" for each c	condition that applies to each	ı lid	
		er Lid		ver Lid	
0=None 1=Irregular Lid Margin 2=Vascular Engorgement 3=Ant/Post Replacement of	OD Yes No Yes No Yes No	OS Yes No Yes No Yes No	OD Yes No Yes No Yes No	OS ☐ Yes ☐ No ☐ Yes ☐ No ☐ Yes ☐ No	
Mucocutaneous Junction	☐ Yes ☐ No	☐ Yes ☐ No	☐ Yes ☐ No	☐ Yes ☐ No	

[figure not shown]

FORM 4: OCULAR ASSESSMENT - Page 2 of 2

Corneal Fluorescein Staining Grading

Enter the staining grade for each segment of each eye

0 = Normal; No staining

1 = Mild; Superficial staining, micropunctate staining

2 = Moderate; Macropunctate staining with some coalescent areas

3 = Severe; Numerous macropunctate areas and/or patches

Manifest Refraction	+/-	Sphere	Cylinder	Axis
OD				X
OS			-	X
Keratotomy	OD			OS
Steep	D	0		D0
Flat	D	0		D0
Eve Temperature Assessment		OD	OS	
1st Reading - Pre-Treatment and Post-	-Treatment			
Corneal Temp (close eye for 5 sec, the	n open)			_
Surrounding Tissue Temp (close eye for	or 5 sec)			
2nd Reading - Post-Treatment Only	_			
Corneal Temp (close eye for 5 sec, the	n open)			_
Surrounding Tissue Temp (close eye f	or 5 sec)			
3rd Reading- Post-Treatment Only				_
Corneal Temp (close eye for 5 sec, the	n open)			_
Surrounding Tissue Temp (close eye for	or 5 sec)			_

FORM 5: PAIN/DISCOMFORT ASSESSMENT- Page 1 of 1

Assessment Date (DD-MMM-YYYY)				
Assessment Timeframe	☐ Pre-Treatment ☐ Post-Treatment ☐ Follow-Up			
Assessment Intertaine	☐ Other, please specify:			
	OD	os		
Subject's pain level (scale 0-10)				

Score	Level of Discomfort/Pain	Description to Anchor Subjective Response	
0	No discomfort or pain	Minimal recognition of pressure only. Equal to the touch of a finger on the skin. Awareness but no discomfort.	
2	Slight or transient awareness of pressure without pain	Pressure tolerable and could be endured indefinitely without compromise to daily activities. Examples: bruise; medical injection; wearing dress shoes, which one would wear all day and might forget to remove when returning home; poorly adjusted glasses.	
4	Moderate discomfort with minimal pain	Discomfort but tolerable. Examples: eye irritation from chlorine pool; pulled muscle; wearing tight dress shoes, which might be worn all day, but would definitely be removed when arriving home; smoke in eye; soap in eye; tight collar or clothes	
6	Moderate pain	Constant awareness of moderate pain affecting daily activities. Examples: corneal abrasion; wearing tight dress shoes, which could not be worn for more than several hours due to excess pressure and pain; wasp or hornet sting.	
8	Severe pain	Partially debilitating. Examples: broken bone; wearing tight dress shoes, which result in open blisters, making walking more than a few steps impossible; stepping on a nail.	
10	Intolerable pain	Totally debilitating, preventing any activity. Examples: back pain preventing any movement; scalding water; severe migraine; slamming car door on finger; stick in eye.	

Investigator Signature:	Date:	Page 49 of 65-
mivestigator signature.	 Date.	

SUBJECT ID:	_

FOR	RM 6: iLux PRO	CEDURE- Page	1 of 1
Procedure Date (DD-MMM-YYYY) Preparation for iLux Use		If no to any que	estion below, please explain:
Eye makeup removed?	☐ Yes ☐ No		
Contact lenses removed?	☐ Yes ☐ No		
iLux prepared per Directions for Use?	☐ Yes ☐ No		
Anesthetic eyedrops applied to each eye?	☐ Yes ☐ No		
Baseline temperature measured?	☐ Yes ☐ No		
iLux serial number			
iLux disposable lot number		-	
iLux Treatment	OD	OS	
#1: Central-temporal lower eyelid			Explain any ND below
Heating Time (sec)			□ ND
Holding Force (lbs.)			□ ND
Maxiumum Temperature (°C)			□ ND
#2: Central-nasal lower eyelid			
Heating Time (sec)			□ ND
Holding Force (lbs.)			□ ND
Maxiumum Temperature (°C)			
#3: Central-temporal upper eyelid			
Heating Time (sec)			□ ND
Holding Force (lbs.)			□ ND
Maxiumum Temperature (°C)			□ ND
#4: Central-nasal upper eyelid			 
Heating Time (sec)			□ ND
Holding Force (lbs.)			□ ND
Maxiumum Temperature (°C)			□ ND
Were there any adverse events during treatment?		☐ Yes ☐ No	If Yes, please fill out AE Form
Were there any device events during treatn		☐ Yes ☐ No	If Yes, please fill out DER Form
Investigator Signature:			Date:Page 50 of 65

SUBJECT ID:	_
DUDUECT ID.	

EODM 7. Huy HSADH ITV ASSESSMENT Dogs 1 of 1			
FORM 7: iLux USABILITY ASSESSMENT - Page 1 of 1			
Were you able to turn the iLux Device On and Off?	☐ Yes ☐ No		
Were you able to read the screen on the iLux clearly without difficulty?	☐ Yes ☐ No		
Were you able to remove the disposable from the packaging and load the disposable into the device as instructed by the User's manual?	☐ Yes ☐ No		
Were you able to apply pressure to the eyelid without difficulty?	☐ Yes ☐ No		
Were you able to apply heat to the eyelid without difficulty?	☐ Yes ☐ No		
Were you able to view the eyelid margin with the magnifier without difficulty?	☐ Yes ☐ No		
Were you able to recharge the battery as described in the User's manual?	☐ Yes ☐ No		
For an answer of "No" above, please provide additional details below:			

FORM 8: ADVERSE EVENT- Page 1 of 1

Timepoint of adverse event:	☐ Treatment ☐ Post-Treatment ☐ Follow-Up☐ No Adverse Events for this Subject
Date adverse event began (DD-MMM-YYYY)	
Time adverse event began (24-hour format, HH:MM)	:
Was the event a serious adverse event (SAE)? If Yes, indicate which criteria meets the protocol definition of SAE Led to death Led to serious deterioration in the health of the patient that resulted in: - A life-threatening illness or injury - A permanent impairment of a body function - In-patient or prolonged hospitalization - Medical or surgical intervention to prevent life-threatening illness or injury or permanent impairment to body structure or a body function Was the event device-related? Was the event procedure-related? Was the event an unanticipated adverse event?	☐ Yes ☐ No ☐ Related ☐ Not Related ☐ Related ☐ Not Related ☐ Yes ☐ No
Event severity	☐ Mild ☐ Moderate ☐ Severe
Diagnosis of adverse event:	
Treatment or action taken to treat adverse event:	□ None □ OTC/Rx Drug □ Non-Drug Treatment/Procedure □ Hospitalization/ER Visit
Action taken during procedure:	☐ None ☐ Study Procedure Interrupted ☐ Study Procedure Discontinued
Outcome of event:	☐ Resolved without sequelae ☐ Resolved with sequelae (specify below) ☐ Ongoing ☐ Death ☐ Unknown
Date of resolution:	Time of resolution:: □ N/A
Briefly describe the event, including any sequelae:	
Investigator Signature:	Date:Page 52 of 65

SUBJECT ID:	_
-------------	---

FORM 9: DEVI	CE EXPERIENCE REPO	RT FORM- Page I of I
Date of event (DD-MMM-YYYY)		
Time of event (24-hour format, HH:MM)	:	-
Did the event result in an adverse event?	☐ Yes ☐ No	If Yes,please fill out an AE Form
Device(s) involved in the event (check all that apply):	☐ iLux Instrument ☐ iLux ☐ QC Checkor ☐ Magnifie	Disposable ☐ Batteries ☐ Charging Stand
	☐ Other, please specify:	
Type of event (check all that apply):	☐ Product Damaged ☐ No☐ Compression Malfunction	it Won't Turn On Software Malfunction Temperature Increase Temperature Cutoff LED Malfunction Display Malfunction Disposable Won't Engage with Unit
	☐ Other, please specify:	
Action taken during procedure:	☐ None ☐ Study Procedure	E Interrupted Study Procedure Discontinued
Device disposition:	☐ Continued with Original I	Device Device Used
Briefly describe the event:		
Investigator Signature:		Date: Page 53 of 65-

